## **Objectives**

1. To evaluate the effectiveness of a collaborative stepped care and peer support programme in engaging older people at-risk of or with depression.
2. To evaluate the efficacy of the programme in reducing symptoms/risks and promoting wellbeing in older people at-risk of or with depression.
3. To investigate the impact of the programme on care resources utilization in these older adults.

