### Participants

1. Intervention Group: older people at-risk of having depression (n=1,600) and those with clinically significant depressive symptoms (n=400) recruited from NGOs providing the intervention in four pilot districts in Hong Kong
2. Control Group: older people at-risk of having depression (n=400) and those with clinically significant depressive symptoms (n=100) referred by different NGOs in Hong Kong and recruited through open recruitment

The inclusion criteria are:

- age 60 years or above; and
- residing in Kwun Tong, Kwai Chung, Tseung Kwan O, or Sham Shui Po; and
- have one or more known risk factor(s) for developing depression; and/or
- have depressive symptoms of mild level or above; and
- able to give informed consent to participate

The exclusion criteria are:

- known history of autism, intellectual disability, schizophrenia-spectrum disorder,
- bipolar disorder, Parkinson's disease, or dementia
- (temporary exclusion criteria) imminent suicidal risk;
- and difficulty in communication

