#### Assessment Procedures

After basic screening, assessments will be conducted by trained social services staff and peer supporters employed by NGOs for the intervention group, and by trained research assistants employed by the University of Hong Kong for the control group.

For the intervention group, assessments will be conducted at baseline (T0/Intake), completion of intervention (4 weeks to 6 months, depending on individual condition) or drop-out (T1/Exit), and follow-up at 12 months (T2/FU). For control group, assessment would be conducted at T0 and T2.

Assessment for those with clinically significant depressive symptoms will last for about 90 minutes, and assessment for those at-risk of depression will last for around 60 minutes.

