#### Interventions

The intervention group will receive a collaborative stepped care programme provided by registered social workers and trained peer supporters from elderly or mental health service units (NGOs) according to level of risks, symptom severity, and intervention response. Home visits or other format of contact will be delivered by trained peer supporters employed by NGOs to detect and engage hidden cases.

For “at-risk” group, 4 weeks of “selective prevention” group sessions will be provided at the elderly service level by trained peer supporters with registered social worker supervision, on wellness topics tailored to the person’s concern as entry point, packaged with mental health information, followed by a review. If the review shows no significant improvement, a further 2-4 weeks of group plus individual casework sessions will be provided.

For people with depressive symptoms, we further divide them to “mild” and “moderate” groups. For mild group, 6-8 weeks of indicated prevention with psychoeducation or low-intensity psychotherapy would be provided. For moderate group, 6-8 weeks high- intensity cognitive behavioral therapy (CBT) would be provided. All intervention for depressed elderly would be conducted by registered social workers who are trained by this project and employed by the NGOs. The trained peer supporters will be matched to individual older adults to walk them through the process.

The control group will receive treatment as usual, which will be determined by the responsible worker from NGO units.

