9. EQ-5D-5L (Herdman et al., 2011): a measure of health-related quality of life at five dimensions (5D), each with five levels (5L) of problems, and the five dimensions are: mobility, self-care, usual activities, pain/discomfort, and anxiety/depression. The traditional Chinese version for Hong Kong developed by EuroQol Group would be used.
10. Lifeengagement: a semi-structured interview asking clients about their typical day activities in three domains, physical, social, and mental. A combination of being active in at least two domains would be used as one of the exit criteria.
11. Client Service Receipt Inventory (CSRI) (Chisholm et al., 2000): to collect the current types and level of services which comprise the care package of each participant, and a locally adapted short version would be developed for this purpose.

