### Data Analysis

We will generate descriptive statistics of the demographic and clinical variables at the baseline (T0/Intake) assessment. The independent sample t-test will be used to compare the means of continuous variables in the intervention and control groups; the chi-square test will be used to compare categorical variables; and Fisher exact test will be used for variables with low cell counts ( $n < 5$ ). For the majority of clinical scales that are ordinal in nature, the independent samples Mann-Whitney U-test will be used to examine whether the same distributions could

be assumed across groups. As observations at two /three time points are nested within individuals and individuals are nested within clusters (centers), changes in outcome measures, including PHQ-9 and GAD-7 scores, will be assessed by a three-level linear mixed model. Because the number of clusters is small, degree-of-freedom correction using the Satterthwaite method will be applied to the mixed models to maintain the desired type I error rate (Leyrat, Morgan, Leurent, & Kahan, 2017). We will use STATA 14.1 (StataCorp, 2015) for data analysis. For all the tests, the statistical significance level was set at .05.

To investigate engagement in the intervention versus control group, the following analyses will be conducted: (1) Cox proportional hazard regression analysis of the time to the primary endpoint of voluntary withdrawal from service; (2) Chi-square test of initial refusal of service by eligible participants after screening.

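### The between-arm Cox model of time to voluntary withdrawal has no planned event dates, time zero or end of risk in the control arm

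*Combined protocol and SAP*

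**What the plan says.** All references are to the combined protocol and SAP.

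- **Objectives.** The first objective is "To evaluate the effectiveness of a collaborative stepped care and peer support programme in engaging older people at-risk of or with depression".
- **Data Analysis.** Engagement is compared between arms in two ways: "Cox proportional hazard regression analysis of the time to the primary endpoint of voluntary withdrawal from service", and "Chi-square test of initial refusal of service by eligible participants after screening". No other endpoint in the text available is called primary.
- **Assessment Procedures.** After baseline, the intervention arm is assessed at "completion of intervention (4 weeks to 6 months, depending on individual condition) or drop-out (T1/Exit), and follow-up at 12 months (T2/FU". The next sentence reads: "For control group, assessment would be conducted at T0 and T2".
- **Interventions.** "The control group will receive treatment as usual, which will be determined by the responsible worker from NGO units". No start, length or completion of that care is given.
- **Measurements, item 11.** The only service-use instrument, the CSRI, is "to collect the current types and level of services which comprise the care package of each participant". No stop date or reason for stopping is mentioned.
- **Participants.** Controls are "referred by different NGOs in Hong Kong and recruited through open recruitment".

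No section states a censoring rule, an interval-censored method, or a plan to take withdrawal dates from unit records.

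**The concern.** A Cox comparison needs three things in each arm: a time zero, a date for each event, and a rule for when a person stops being at risk. The intervention arm has a reasonable source for all three: intake, and an exit assessment at completion or drop-out. The control arm has none of them. Its participants are seen twice, 12 months apart, and usual care has no stated beginning or end.

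This model is one of only two planned tests of engagement, which is the first objective. If the plan is followed as written, the analyst will have intervention withdrawals dated within the first six months and control withdrawals with no date, and will have to settle the coding after the data are in. Two questions are then open: how to date control events, and whether people who complete the programme stay at risk afterwards. Each can move the hazard ratio a long way when the arms do not differ.

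**Working it through.** The plan gives no event count, withdrawal rate, hazard ratio or power for this analysis, so there is no stated figure to reproduce. The check is whether the model recovers a hazard ratio (HR, intervention over control) of 1 when withdrawal is truly the same in both arms.

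**Inputs from the documents.** Intervention 1,600 + 400 = 2,000; control 400 + 100 = 500 (Participants). Exit at 4 weeks to 6 months; controls seen at 0 and 12 months (Assessment Procedures). Courses: at-risk 4 weeks, plus 2 to 4 more if there is no improvement; mild and moderate 6 to 8 weeks (Interventions).

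**Assumed.** Constant withdrawal hazard h of 0.5%, 1% or 2% per week in both arms; course length uniform over 4 to 26 weeks unless stated; no clustering; 400 runs per cell.

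| Coding | HR at h = 0.5 / 1 / 2% |
|---|---|
| (a) Exact dates in both arms, completers censored at completion | 1.01 / 1.01 / 0.99 |
| (b) Control events dated at week 52, or at week 26; completers censored | infinite in every run |
| (c) Control events dated at week 52; completers carried event-free to week 52 | 0.33 / 0.38 / 0.48 |
| (d) As (c), but with exact control dates | 0.31 / 0.32 / 0.36 |

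In (c) and (d), p<0.05 in 100% of runs; in (a), in 4.8%, 7.2% and 4.8%.

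**Why (b) is infinite.** All intervention time at risk ends by week 26, so a control event placed at week 26 or 52 has no intervention participant at risk and contributes nothing. Every contributing event is an intervention event, and the partial likelihood is a product of terms e^β / (n1·e^β + n0), where n1 and n0 are the numbers at risk. It rises without limit in β. In a separate run (12-month withdrawal of 10%, 20% or 40%, 60 replicates each), a log-rank test on data coded this way rejected in every replicate, against the programme.

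**Why (c) and (d) fall below 1.** Intervention events can occur only during the course; control events can occur over all 52 weeks.

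- Withdrawing during a 4-to-26-week course: 1 − (e^(−4h) − e^(−26h)) / (22h) = 7.2%, 13.8%, 25.3%.
- Withdrawing over 52 weeks: 1 − e^(−52h) = 22.9%, 40.5%, 64.7%.
- Ratio: 0.31, 0.34, 0.39, with identical hazards.

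**With the course lengths under Interventions.** Assume half the at-risk group is extended: 800 people have 4 weeks and 800 + 400 = 1,200 have 6 to 8 weeks (mean 7). At 1% per week, expected withdrawals are 800 × (1 − e^(−0.04)) + 1,200 × (1 − e^(−0.07)) = 31.4 + 81.1 = 112.5, or 5.6% of 2,000. The ratio to 40.5% is 0.14. Simulated HRs at 1% are 0.14 for coding (c) and 0.12 for (d). Over the three hazards the range is about 0.1 to 0.2.

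Row (d) separates two faults. Missing control dates produce (b). The low HRs come from the end-of-risk rule and remain when control dates are exact.

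**The case against.** **The units probably hold dates.** Withdrawal is a service event, whereas Assessment Procedures schedules research assessments. Some controls are referred by NGOs, and usual care has a responsible worker, so dated records are plausible. This stands as far as it goes: the dates may exist. But no section plans to collect them, or says which service an openly recruited control would withdraw from.

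**The finite biased HRs depend on a coding the plan does not state.** This is correct. Carrying completers event-free to 12 months is one possible choice, and a reader might infer from rows (c) and (d) that the plan is built to favour the programme. The documents do not support that. They show only that the end of risk is left open.

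**An infinite HR would be noticed.** Probably so, but noticing it does not supply the dates.

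**Other methods exist.** An interval-censored model still needs a defined service, event and end of risk in controls, plus withdrawal status at 12 months. A comparison of proportions withdrawn needs a common time; with controls seen only at 0 and 12 months that is 12 months, after intervention courses have ended. Neither is planned.

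**Openly recruited controls may have no service.** A reader might infer that they cannot withdraw at all. The documents do not say this: they give controls a responsible worker, and the refusal test implies an offered service. The point does not depend on it.

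**Conclusion.** The point holds and should be corrected. Under the planned data collection, a control withdrawal is known at best to fall within 12 months, so the between-arm Cox model has no valid control event times. The two obvious stand-in dates, 12 months and its 26-week midpoint, both give an infinite HR under a true null. This follows from the schedule at any hazard, provided completers are censored at completion.

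The unstated end of risk is a second, separate gap. Its possible size is an HR of about 0.3 to 0.5 (4-to-26-week courses) or 0.1 to 0.2 (4-to-8-week courses) when the truth is 1. That rests on constant equal hazards, the assumed course lengths and a coding the plan does not propose.

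The finding does not reach the PHQ-9 and GAD-7 mixed models. Nor does it show that the engagement result would be biased in a known direction, because that depends on choices not yet made.

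**What to change.** 1. **Data Analysis.** Define for each arm the service, time zero, the event (the participant's own decision, separate from completion or case closure) and the end of risk. Censor at completion and use one common window for both arms, no later than 26 weeks.
2. **Assessment Procedures.** Record the date and reason of stopping in the same way in both arms, from the NGO unit record first, with a question at 12 months as back-up. Record recruitment route and NGO service use at baseline. Limit the between-arm comparison to people with a service at baseline or intake.
3. **If only baseline and 12-month status can be had for controls,** drop the between-arm Cox model and report withdrawal in the intervention arm descriptively. Do not substitute service contact at 12 months: planned completion would count as non-contact in one arm only.

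**Costs and limits.** No new visit is needed. The added questions take about 2,500 × 2 minutes (assumed) ÷ 60 = 83 staff hours; record extraction is extra and not costed here.

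A 12-month question misses people lost before then. If 20% or 40% of control withdrawers are missed (assumed; 1% per week, 4-to-26-week courses), the HR is about 1.18 or 1.45 when the truth is 1. As a check, if missed withdrawers drop out of the data, the HR at week t is [1 − m(1 − e^(−h(52−t)))] / (1 − m), where m is the share missed. From week 0 to week 26 this runs from 1.15 to 1.19 for m = 20%, and from 1.40 to 1.51 for m = 40%. This is why unit records come first, and why a sensitivity analysis for missed withdrawers should be reported.

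Precision is modest. With exact dates and 4-to-8-week courses at an assumed 1% per week, the 95% simulation range under no effect is about 0.7 to 1.5, before any allowance for clustering. Controls already in service at baseline differ from new programme starters, so the contrast remains imperfect even with good dates.
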